8.2.3 Specimen Preparation, Handling, and Shipping

8.2.3.1 Instructions for Specimen Preparation, Handling, and Storage

The collected PK blood samples (3 mL) will be placed on ice after blood draw, and within 1 hour centrifuged at room temperature at approximately 3000 revolutions per minute for 15 minutes. Plasma will then be harvested and split into 3 aliquots of approximately 250 μ L (any additional plasma placed in a fourth tube as a back-up sample) and stored frozen at -20°C until shipped.

Analysis of plasma for UV-4 will be performed by the qualified bioanalytical laboratory,

Instructions for the proper preparation, handling, storage and shipping of specimens will be provided separately in a study-specific laboratory manual (i.e., Bio-packet).

8.2.3.2 Specimen Shipment

Details regarding shipment of plasma samples can be found in the laboratory manual.

8.3 Diet, Exercise, and Study Restrictions

Enrolled subjects will be advised to abstain from strenuous exercise starting 96 hours (4 days) prior to dosing on Day 1 and continuing through the in-subject stay and for at least 96 hours prior to the follow-up visits. In addition, enrolled subjects will be advised to stop consumption of caffeine-containing beverages (e.g., coffee, tea, cola, energy drinks, and cacao [chocolate]) for 72 hours before first dose and refrain from using them during the in-subject stay(s) of the study. Alcohol consumption will not be allowed during the entire study (from 72 hours before dosing through follow-up). Additional food and drinks that are not permitted 72 hours prior to and during the in-subject treatment period of the study are grapefruit or grapefruit juice, Seville oranges or orange marmalade.

Subjects will be instructed to maintain a diet that will assist in preventing a false positive reading for fecal occult blood. Such a diet excludes: red meat (no beef, lamb, or liver in any form) and vegetables high in peroxidase (turnips, radishes, and horseradish). Vitamin C is limited to ≤ 250 mg/day. Subjects will be given a diet guideline at screening. Subjects will be advised that if accepted for the study they should follow the dietary guidelines for fecal occult blood 72 hours prior to check-in.

Enrolled subjects will remain in the study unit from the time of admission on Day -1 until discharge from the unit on Day 8. During that period of time they will consume a normal house diet (defined as a standard diet that doesn't allow for substitutions and is received by all subjects) served at standard times (breakfast, lunch, and dinner) and will have access to snacks as permitted.

Prior to dosing on Day 1, subjects will not eat any food at least 3 hours before the first dose. Consumption of water and food will not be restricted except for 1 hour before to 1 hour after dosing for all subsequent doses (except for approximately 240 mL (total volume) allocated for study product solution plus rinse and water). Lunch, dinner, and an evening snack will be provided.

During the follow-up period it is recommended that subjects continue eating a balanced diet, and avoid consumption of caffeine-containing beverages.

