7.3 Treatment Period

The specific order of evaluations conducted during the treatment period will be defined by the [REDACTED] Biometrics system.

7.3.1 Day 1

Prior to the administration of the first dose of study product, the following procedures will be performed:

- Brief physical examination focused on the examination of skin and oropharyngeal mucosa for evidence of bleeding and/or bruising (oral [gums] and evidence of hematoma, ecchymosis or petechia), brief neurological examination (mental status, motor system, and sensory system);
- Confirm that subject adhered to fasting requirements of at least 3 hours before the first dosing;
- Obtain vital signs (blood pressure, pulse rate, after being supine for 10 minutes, and orthostatic blood pressure and pulse rate (taken after 2 minutes in the standing position), respiratory rate and oral temperature;
- Obtain a triplicate 12-lead ECG;
- Obtain baseline blood sample for PK analysis ($t=0$), to be taken within 1 hour prior to first dose;
- Telemetry starting at -0.5 hours on Day 1 through at least 4 hours post the first dose;
- Randomization

All subjects will be administered the assigned study product or placebo. The total volume of each dose of the study product solution plus the rinse(s) and water will be 240 mL.

- The following procedures will be instituted to reduce incomplete or interrupted dosing of subjects:
In the event of partial dosing, either due to dosing error, or the subject coughing, gagging or spilling solution, the subject will only be followed for safety measurements as defined in [Section 5.3.3](#).

Following the administration of study product, the following procedures will be performed:

All physical exams, blood tests and ECGs after subjects have been dosed are obtained at approximately the same time each morning (within 2 hours).

- Obtain clinical chemistry, hematology, and coagulation;
- Obtain blood samples for PK analysis at 0.25 (± 5 min), 0.5 (± 5 min), 1 (± 10 min), 1.5 (± 10 min), 2 (± 10 min), 2.5 (± 15 min), 3 (± 15 min), 5 (± 30 min), 6 (± 30 min), 8 (± 30 min) hours (8 hour sample to be collected immediately before the second dose).
- Obtain vital signs (blood pressure and pulse rate including oral temperature and respiratory rate) at 1, 2, 3, 4, 5, 6 and 7 hours (± 15 minutes), after each administration of the study product. Vital signs should be taken after being supine for 10 minutes,

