and orthostatic blood pressure and pulse rate (taken after 2 minutes in the standing position);

- Telemetry through at least 4 hours post first dose;
- Obtain fecal occult blood assessment starting approximately 6 hours post first dose on every stool sample. Stool volume and frequency will be recorded;
- Obtain occult blood on all vomitus;
- Perform brief physical examination focused on the examination of skin and oropharyngeal mucosa for evidence of bleeding and/or bruising (oral [gums] and cutaneous) 30 (+ 15) minutes after the first dose;
- Review concomitant medication usage once daily;
- Completed AE assessment (including SAEs) will be recorded on AE source forms throughout the study and placed in the subject's clinic records.

Subjects will receive standardized meals as follows on Day 1: lunch 4 hours post first dose and dinner after completion of procedures scheduled at those times; subjects will also receive a light evening snack. A drink will also be provided with each of the meals. No breakfast will be served on Day 1. Dosing will occur TID every 8 hours \pm 0.5hour.

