7.3.2 Day 2 through Day 7 (In-Clinic)

All subjects will be administered the assigned study product or placebo according to the dosing schedule. If a subject has a missed or incomplete dose as described above ([Section 7.3.1](#)) the subject will continue to the next dose as planned. Subjects will not be allowed to miss more than four (4) doses after achieving predicted steady state (i.e. after the third dose on day 1) while participating in the study. If a subject misses four (4) or less doses their continued participation in the study will be determined by the PI and the Emergent and NIAID medical monitors on a case by case basis.

As per Section 7.3.1, all physical exams, blood tests and ECGs after subjects have been dosed are obtained at approximately the same time each morning after dosing (within 2 hours).

- Brief physical examination focused on the examination of skin and oropharyngeal mucosa for evidence of bleeding and/or bruising (oral [gums] and cutaneous); symptom directed/targeted examination based on subject symptoms and brief neurological examination (mental status, motor system, and sensory system);
- Obtain vital signs (blood pressure, pulse rate), after being supine for 10 minutes, and orthostatic blood pressure and pulse rate (taken after 2 minutes in the standing position), respiratory rate and oral temperature;
- Obtain clinical chemistry, hematology, coagulation, and urinalysis;

- Obtain fecal occult blood assessment on every stool sample or less frequent as per discretion of the PI. Stool volume and frequency will be recorded;
- Obtain occult blood on all vomitus
- Obtain 12-lead ECG at same time each day (within 2 hours); telemetry starting 0.5 hours prior to the third (3rd) dose on Day 7 continuously through 4 hours post dose;
- Obtain blood samples for PK analysis Days 2-6: one trough sample daily within fifteen (15) minutes before the first dose approximately the same time each day (± 10 min);
- Obtain blood samples on Day 7: immediately (within fifteen minutes) before the final dose, and at 0.25 (± 5 min), 0.5 (± 5 min), 1 (± 10 min), 1.5 (± 10 min), 2 (± 10 min), 2.5 (± 15 min), 3 (± 15 min), 5 (± 30 min), 6 (± 30 min), 8 (± 30 min), 10 (± 30 min), 12 (± 30 min), and 14 (± 30 min) hours after the final dose;
- Review concomitant medication usage;

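### Does a 3-hour fast before the first dose, but only a 1-hour food rule around the last, spoil the accumulation ratio?

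*Protocol*

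**What the plan says.** AR is defined the same way in Protocol 11.4.6 and SAP 10.5.1: AUC(0-8) after the last dose over AUC(0-8) after the first. Protocol 3.2.2 and SAP 5 list it among the secondary outcomes.

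**First dose, Day 1.** Protocol 8.3: "Prior to dosing on Day 1, subjects will not eat any food at least 3 hours before the first dose". Protocol 7.3.1 has the site check this ("Confirm that subject adhered to fasting requirements of at least 3 hours before the first dosing"), adds "No breakfast will be served on Day 1", and sets the meals: "Subjects will receive standardized meals as follows on Day 1: lunch 4 hours post first dose".

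**All later doses, including the final one on Day 7.** Protocol 8.3: "Consumption of water and food will not be restricted except for 1 hour before to 1 hour after dosing for all subsequent doses". The house diet is "served at standard times (breakfast, lunch, and dinner) and will have access to snacks as permitted".

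**Sampling.** Protocol 7.3.2 asks on Days 2 to 6 for "one trough sample daily within fifteen (15) minutes before the first dose approximately the same time each day". The Day 7 profile begins "immediately (within fifteen minutes) before the final dose", which is the third dose of that day. SAP 10.5.1 takes AUC(0-8) only from the Day 1 first dose and the Day 7 final dose. It also derives AUC(0-24) as three times the final-dose AUC(0-8), and CL/F as dose divided by that AUC(0-8).

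**The concern.** A ratio of two exposures measures accumulation only if the conditions of the two intervals are otherwise alike. Here the denominator comes from a fasted morning dose. The numerator comes from a dose around which food is barred for only 1 hour on each side, and which falls about 16 hours later in the dosing day. If food or time of day altered the absorption or clearance of UV-4, AR would report that as more or less accumulation. Neither document plans a matched meal, a record of food times or a caveat. The Protocol Summary says the PK results are meant to help with later dose calculations, so a distorted AR could carry forward.

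**Working it through.** **1. Are there really only two AUC profiles?** Day 1: pre-dose plus 10 samples = 11. Days 2 to 6: 5 troughs. Day 7 into Day 8: pre-dose plus 13 = 14. Day 10: 1. Total 11 + 5 + 14 + 1 = 31, which matches the 31 PK samples in Protocol Table 6. No other interval can give an AUC(0-8).

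**2. How different are the food conditions?** On Day 1 no meal is scheduled from 3 h before to 4 h after the dose, a span of 3 + 4 = 7 h. On Day 7 food is barred for 1 + 1 = 2 h. These two figures are not like for like: the first is a meal schedule and the second is a permission. Protocol 7.3.2 places post-dose examinations in the morning after dosing, so the first daily dose is a morning dose. If it is given between 06:00 and 09:00 (an assumption; no clock times are stated), the third falls between 22:00 and 01:00 and its 8 hours run overnight. The listed meals are breakfast, lunch, dinner and an evening snack. By schedule, then, the Day 7 interval may hold little or no food, while the Day 1 interval contains lunch. The real contrast is unknown, even in direction.

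**3. What would an effect do to AR?** The documents give no half-life, absorption rate or food effect, so all inputs here are assumptions.

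- Half-life 3.2 to 7.2 h. Protocol 7.3.2 predicts steady state after the third dose. Taking that as 16 to 24 h and 3.33 to 5 half-lives gives 16/5 = 3.2, 24/5 = 4.8 and 24/3.33 = 7.2.
- Absorption rate constant ka of 2, 1 and 0.5 per hour.
- One compartment, 21 doses every 8 h, superposition.
- Relative availability f = 0.8 or 1.25 for affected doses.

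Let AR0 be the ratio with no effect. The share of the numerator carried over from earlier doses is 1 - 1/AR0.

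- Every later dose affected: AR = f x AR0, a shift of -20% or +25%.
- Final dose only affected: AR = AR0 - 1 + f.

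**4. What would matching only the final dose to the Day 1 fast do?** If f still acts on doses 2 to 20, AR = 1 + f(AR0 - 1). AUC(0-24) and CL/F come from the same interval and should be compared with uniform dosing under the 1-hour rule, f x AR0.

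Worked case, half-life 4.8 h, ka 1/h, f = 0.8: AR0 = 1.5825. Matched AR = 1 + 0.8 x 0.5825 = 1.466, and 1.466/1.5825 = 0.926, so AR is still off by -7.4%. The uniform value is 0.8 x 1.5825 = 1.266, and 1.466/1.266 = 1.158, so AUC(0-24) is off by +15.8% and CL/F by 1/1.158 - 1 = -13.6%.

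Ranges over ka = 2 to 0.5 per hour; pairs are f = 0.8 / f = 1.25:

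| Half-life | AR0 | Carry-over | AR shift, final dose only affected | AR error left after matching | AUC(0-24) error after matching | CL/F error after matching |
|---|---|---|---|---|---|---|
| 3.2 h | 1.25 to 1.42 | 20 to 30% | -16.0 to -14.0% / +20.0 to +17.6% | -4.0 to -6.0% / +5.0 to +7.4% | +20.0 to +17.6% / -16.0 to -14.0% | -16.7 to -14.9% / +19.1 to +16.3% |
| 4.8 h | 1.51 to 1.77 | 34 to 44% | -13.2 to -11.3% / +16.5 to +14.1% | -6.8 to -8.7% / +8.5 to +10.9% | +16.5 to +14.1% / -13.2 to -11.3% | -14.2 to -12.4% / +15.2 to +12.7% |
| 7.2 h | 1.95 to 2.32 | 49 to 57% | -10.3 to -8.6% / +12.8 to +10.8% | -9.7 to -11.4% / +12.2 to +14.2% | +12.8 to +10.8% / -10.3 to -8.6% | -11.4 to -9.7% / +11.4 to +9.4% |

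**5. What can already be checked?** An AR predicted from the Day 7 terminal slope, 1/(1 - exp(-8 x lambda_z)), gives 1.21, 1.46 and 1.86 at the three half-lives, to set against the observed value. The Day 7 pre-dose sample against its 8 h sample shows whether the final dose behaved unlike the one before it. The Days 2 to 6 troughs show whether a plateau was reached. Day 1 and Day 7 tmax respond to slower absorption: a fall in ka from 2 to 0.5 per hour at the final dose moves the sampled tmax from 1.0-1.5 h to 2.5 h and AR by -8 to -10%. SAP 10.5.1 allows additional PK parameters where appropriate.

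**The case for a change.** The strongest case for a change is that the mismatch is real and could have been avoided, and that the checks in step 5 are indirect. The slope-based prediction assumes instant absorption and runs low when absorption is slow: at 4.8 h with ka 0.5 per hour it gives 1.46 against 1.77. A pure change in the extent of absorption moves tmax by only about 0.3 h at most, so tmax would largely miss it. The background PK sections are redacted, so a reader cannot rule out a known food effect. The cost would also be small: one diet line, four time fields per subject and a sentence in the SAP.

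Most of this stands as description. AR on its own cannot tell a food or clock-time effect from accumulation. It does not follow that matching is better. With 20 to 57% of the numerator carried over from doses under the 1-hour rule, a matched final dose would represent neither food condition, and the steady-state reading of AUC(0-24) and CL/F depends on doses 2 to 21 being alike. If the effect were confined to the final dose, matching would remove its food part, but the clock-time difference would stay. The opposite route, putting the first dose under the 1-hour rule, would keep all 21 doses uniform on paper. It would give up the controlled first-dose profile and still not align actual meals, because the two doses fall at different times of day. Recording food times or adding a sentence would alter no estimate.

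**Conclusion.** No change to the plan follows. The mismatch in food rules and time of day is real, but the harm is conditional on an effect that the readable documents do not show, and the actual food contrast at the final dose is unknown. Under an assumed -20% or +25% change in availability, AR would shift by -20% or +25% if every later dose were affected, and by -9 to -16% or +11 to +20% if only the final dose were. Matching the final dose would leave 4 to 14% of AR error in the first case and introduce errors of roughly 9 to 20% in AUC(0-24) and CL/F. These sizes rest on the assumed half-lives, absorption rates and one-compartment model. With no food or clock-time effect, AR is unaffected.

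AR is descriptive. It enters neither the escalation step nor the halting criteria (Protocol 9.5 and 9.6), and dose proportionality (SAP 10.6.3) uses Day 7 last-dose data under one food rule in every cohort. Keeping doses 2 to 21 under one rule is a fair trade-off. A pharmacokineticist would ordinarily read AR beside the Day 7 slope, the troughs and tmax, all of which the plan already provides.

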9 ASSESSMENT OF SAFETY

9.1 Specification of Safety Parameters

Safety is the primary objective.

9.1.1 Adverse Events

Adverse events will be evaluated from time of the first dose administration through the last follow-up visit. AEs that have not resolved at the Day 15 (± 1) follow-up visit will be followed until resolution or until medically stable.

9.1.2 Vital Signs

Vital signs (after being supine for 10 minutes) including SBP and DBP (mmHg), pulse rate (beats/minute), respiratory rate (breaths/minute), and oral temperature ($^{\circ}\text{C}$) will be obtained and recorded according to the time points in the schedule of events ([Appendix IV](#)). Systolic and diastolic blood pressure and pulse rate will also be obtained after 2 minutes standing and recorded according to the time points in the schedule of events. If a vital sign measurement is observed to be abnormal, it may be repeated up to a total of 2 times at 5 to 10 minutes intervals. If a normal value is obtained, no further repeat measurements are required. If the value is still abnormal after 2 repeats, the least abnormal value will be utilized for grading the AE. The AE will be considered ongoing until a future measurement shows resolution. The subject may be referred to a primary care provider if the abnormality does not resolve and, according to the study clinicians, requires medical care. Vital sign values of Grade 1 or higher according to toxicity grading criteria listed in [Appendix II](#) will be reported as AEs.

